11.4.3 Secondary Analyses

Secondary analyses focus on the secondary outcomes (see 5.2) and hypotheses (see 11.1).

Crosstabs are used to calculate the proportion of responders ($\geq 30\%$ reduction in SRRS from baseline) across groups. Repeated measures ANOVAs will clarify the time-course of SRRS change from baseline to week 6 (including week 1, 2, 3 and 6) and differences between groups.

Repeated measures ANOVAs will test the change of clinical and motor rating scales between baseline and week 3, week 6, and week 24 and differences between groups.

Linear regression analyses will test the association between neuroimaging markers (resting state perfusion, connectivity, fMRI activation, ect.) and measures of PS at baseline.

Repeated measures ANOVAs will test the longitudinal changes in neuroimaging markers from baseline to week 3.

All analyses will be performed by the PI and his team or collaborators with permission of the PI.

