4.3 Secondary Objectives

The study further seeks to determine, whether lf-rTMS (inhibitory) will be superior over placebo or iTBS (facilitatory) in all clinical and motor behavioral measures, e.g. greater reduction in BFCRS scores from baseline, greater increase in activity levels, or finger taps. In addition, the study will test the effects of rTMS on the cerebral motor network connectivity and activity, as well as on cerebellar function and motor cortex excitability. Furthermore, the study will explore the neuroimaging markers of response to treatment. Moreover, the study will test the association between measures of PS and neuroimaging markers of the motor system, e.g. network connectivity, activity, and structure. Next, the study will investigate the temporal dynamics of PS by comparing a waiting list group to the placebo group. Finally, the study will test whether lf-rTMS treatment for 3 weeks will have lasting effects on PS at week 6 or 6-months follow-up.

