11. STATISTICAL METHODS

A two-tailed p-value of $< .05$ is considered to be statistically significant in all analyses. We will also report effect sizes for the comparisons of primary and clinical secondary outcome variables between groups.

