Hypothesis 4a: patients receiving inhibitory rTMS will have better outcome (less PS, less general symptom severity) shortly after the intervention (at 6 week follow-up) compared to patients receiving placebo or facilitatory iTBS

Hypothesis 4b: patients receiving inhibitory rTMS will have better outcome (less PS, less general symptom severity) and superior function (social and global) at 6-month follow-up compared to patients receiving placebo or facilitatory iTBS

Hypothesis 4c (exploratory): changes in functional connectivity within the motor system from baseline to week 3 will predict better outcome at week 6, particularly reduced M1-thalamus functional connectivity.

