11.2 Determination of Sample Size

The main effects of the 3-week interventions on PS (SRRS scores) will be calculated in a repeated measures design including 2 measures (Baseline, week 3) and four groups (If-rTMS, iTBS, sham, waiting group-If-rTMS). Assuming a moderate effect size ($f = 0.23$) as indicated by our pilot data in a repeated measures ANOVA with moderate correlation between time points (0.5), a power of 0.95 and an $\alpha = 0.05$, we would need 88 patients (22 per group).

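### For the continuous outcomes, section 11.4.3 specifies no week-6 or week-24 contrast, so its repeated measures ANOVAs do not by themselves establish hypotheses 4a and 4b

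*Combined protocol and SAP*

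**What the plan says.** **The claims are tied to visits.** Section 4.3 asks "whether lf-rTMS treatment for 3 weeks will have lasting effects on PS at week 6 or 6-months follow-up". In section 11.1, hypothesis 4a concerns slowing and general symptoms at the 6-week follow-up. Hypothesis 4b concerns the same outcomes at 6 months and adds "superior function (social and global) at 6-month follow-up compared to patients receiving placebo or facilitatory iTBS". The synopsis (outcome 4) lists change in PANSS, BNSS, SRRS and SOFAS from baseline to 6 months.

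**The analyses are in section 11.4.3.**
- SRRS: "Repeated measures ANOVAs will clarify the time-course of SRRS change from baseline to week 6", with weeks 1, 2, 3 and 6 named as the visits, and differences between groups.
- Other scales: "Repeated measures ANOVAs will test the change of clinical and motor rating scales between baseline and week 3, week 6, and week 24", again with differences between groups.
- SRRS responders: crosstabs across groups. Section 5.2.1 sets the visits for this outcome at weeks 1, 2, 3, 6 and 24.
- GAF, SOFAS and UPSA-brief: no analysis is named. Section 5.3 lists them as other outcomes, measured at baseline and weeks 6 and 24.

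No visit-specific contrast, post hoc test or pairwise comparison with placebo or iTBS is written for any continuous outcome. Section 11 applies one rule throughout: a two-tailed p below .05 "is considered to be statistically significant in all analyses". Section 11.5 handles missing values by LOCF.

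**The concern.** A group-by-time test in a multi-visit ANOVA asks whether the arms differ in any pattern across the visits. It does not say at which visit they differ. An effect that builds up during treatment and is gone at follow-up produces a significant interaction, just as an effect that persists does. If that p-value were taken as evidence for 4a, a purely on-treatment effect could be read as a lasting one.

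Two gaps add to this. The named SRRS model ends at week 6, although 4b and section 4.3 concern slowing at 6 months. For the other scales, the wording leaves the choice between a joint model and separate models open until the data are in.

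**Working it through.** **1. The plan's own figure.** Section 11.2 gives f = 0.23, "as indicated by our pilot data in a repeated measures ANOVA", correlation 0.5 between time points, alpha 0.05, power 0.95, four groups and two time points. For the group-by-time test:

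- λ = f² × N × m / (1 − ρ), with df = (k − 1)(m − 1) and (N − k)(m − 1).
- N = 88: λ = 0.0529 × 88 × 2 / 0.5 = 18.62, df 3 and 84, power 0.957.
- N = 84: λ = 17.77, power 0.947.

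So 88 (22 per arm) reproduces, and it is sized for week 3 only.

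**2. Effect size in SD units.** Assume that only lf-rTMS differs, by d SD at week 3. The squared interaction effects over the 4 × 2 cells sum to (3/4)(1/2)d² = 0.375d², so f = √(0.375d²/8) = 0.2165d. Then d = 0.23/0.2165 = 1.06. The documents give no SRRS standard deviation, so a range of d is shown below.

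**3. The multi-visit test when nothing remains at follow-up.** Three arms are used because 4a and 4b compare lf-rTMS with placebo or iTBS. The waiting group also has no week-1 or week-2 visit (section 9.1.2). With visit pattern p, λ = n × (1 − 1/k) × Σ(p − p̄)² × d² / (1 − ρ), n = 22, k = 3, ρ = 0.5 between all visits.

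- SRRS model, p = (0, 1/3, 2/3, 1, 0) at weeks 0, 1, 2, 3, 6: Σ(p − p̄)² = 1.5556 − 5 × 0.16 = 0.7556, and λ = 22 × (2/3) × 0.7556 × d² / 0.5 = 22.16d².
- Other scales read as one joint model, p = (0, 1, 0, 0) at weeks 0, 3, 6, 24: Σ(p − p̄)² = 0.75, and λ = 22d².

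| Model | df | d = 0.5 | 0.65 | 0.8 | 1.06 |
|---|---|---|---|---|---|
| SRRS, weeks 0/1/2/3/6 | 8, 252 | 0.32 | 0.54 | 0.76 | 0.96 |
| Joint, weeks 0/3/6/24 | 6, 189 | 0.36 | 0.59 | 0.80 | 0.97 |

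With no effect at any visit, simulation gives about 5%.

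**4. Sensitivity to correlation.** The documents give one correlation, so decay over time is an assumption. All figures in this step are simulated with a Greenhouse-Geisser correction.
- Joint model, correlation 0.7 per three weeks: 0.19, 0.61 and 0.93 for d = 0.5, 0.8 and 1.06, lower than in the table.
- SRRS model, correlation 0.5 per three weeks (which keeps the plan's baseline-to-week-3 value): 0.27, 0.49, 0.70 and 0.95 for the four effects, also lower.
- SRRS model, correlation 0.7 per three weeks: 0.43, 0.73, 0.93 and above 0.99. This is higher, because weekly visits are then strongly correlated.

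The size therefore depends on the correlation pattern, but it stays well above 5% throughout.

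**5. A visit-specific contrast.** In the joint-model setting, with the effect at week 3 only, a two-arm comparison of change from baseline rejects in 4.9–5.4% of simulated trials at week 6 and 4.5–5.3% at week 24. Separate baseline-to-visit ANOVAs likewise contain no week-3 data in the follow-up comparison.

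**6. Power of that contrast if the effect persists.** The SD of change is √(2 × (1 − 0.5)) = 1 and the SE is √(2/22) = 0.30. By normal approximation, two-sided 0.05, power is about 0.94, 0.76 and 0.38 for d = 1.06, 0.8 and 0.5.

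**The case against.** The strongest reply is that the plan is less committed to a faulty test than it may look. Much of this stands.

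- A reader might infer that no follow-up comparison is planned at all. Sections 5.2.1 and 11.4.3 contradict that: SRRS responder proportions are compared between groups at weeks 6 and 24. That comparison is visit-specific. It covers only dichotomised SRRS response, not symptoms or function. A four-group version would include the waiting arm, which has received active treatment by week 6.
- The sentence on the other scales can mean separate baseline-to-visit ANOVAs. The primary analysis in section 11.4.2 already has that two-timepoint form, and it lacks the flaw. If SRRS counts among those scales, week 24 would be covered too. The text does not settle either question.
- The SRRS model is described as clarifying a time course, and no decision rule for 4a or 4b is written. That a faded effect would be reported as lasting is a risk left open, not something the plan states.
- A reader might also infer that fading by week 6 is the expected case. Section 2.2 expects effects to last 2–4 weeks after the last session. For arms treated in weeks 0–3 that is about weeks 5–7, so week 6 lies inside the window. The protocol's expectation supports fading only by week 24.

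None of this supplies the missing contrast for the continuous outcomes.

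**Conclusion.** The concern holds in limited form. For continuous outcomes, section 11.4.3 does not by itself establish 4a or 4b. The one explicitly multi-visit model (SRRS to week 6) can be significant from the on-treatment effect alone: about 32% to 96% of trials for week-3 effects of 0.5 to 1.06 SD. That model also omits week 24. The sentence on the other scales has the same flaw under one reading and not under the other, and functioning has no named analysis.

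The stronger statement that the plan cannot show a lasting effect is not supported, because responder comparisons at weeks 6 and 24 are planned and a sound reading of the other ANOVAs is available.

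The figures assume 22 analysed per arm with no dropout, an effect in lf-rTMS only, a linear build-up to week 3, zero effect at week 6 and equal correlation of 0.5. The 1.06 SD follows from f = 0.23 only under that one-arm pattern. These are secondary hypotheses, so the primary analysis is unaffected.

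**What to change.** - Pre-specify lf-rTMS versus placebo and lf-rTMS versus iTBS contrasts of change from baseline at week 6 (for 4a) and at week 24 (for 4b), for SRRS and the symptom scales. Add the functioning scales at week 24. Take the contrasts from an arm-by-visit mixed model or from an ANCOVA at that visit.
- Base any statement about a lasting effect on those contrasts alone, and keep the multi-visit ANOVA as a description of the time course.
- Do not let LOCF carry week-3 values into the week-6 and week-24 contrasts. Otherwise the on-treatment effect returns through the imputed values.
- State whether any multiplicity adjustment applies across the two comparators, two visits and several scales.

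The cost is SAP wording and a few contrasts on visits already scheduled. The follow-up result may be less favourable, and with 22 per arm a persisting effect of 0.5 SD would be detected only about 38% of the time, so estimates with confidence intervals should carry the message.

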11.4.4 Interim analyses

Interim analyses of the primary analysis are planned after enrolment of 10, 20, 30, 40, 50, 60, and 70 subjects. The scope is to estimate whether any adjustments of the treatment arms are necessary. In addition, baseline data can be tested for associations between neuroimaging data and clinical/motor measures after enrolment of 20, 40, or 60 subjects.

All interim analyses are optional and at the discretion of the PI. Interim analyses are conducted by the PI and his team.

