2.9 Early termination of the study

The Sponsor-Investigator may terminate the study prematurely according to certain circumstances, for example:

- ethical concerns,
- insufficient participant recruitment,
- when the safety of the participants is doubtful or at risk, respectively,
- alterations in accepted clinical practice that make the continuation of a clinical trial unwise,
- early evidence of benefit or harm of the experimental intervention

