11.1 Hypotheses

Aim 1: investigate the clinical and functional neural changes following 15 sessions of daily rTMS

Hypothesis 1a (main hypothesis): lf-rTMS (inhibitory) will be superior over placebo or iTBS (facilitatory) in all clinical and motor behavioral measures, e.g. greater reduction in SRRS scores from baseline, greater increase in activity levels, or coin rotations.

Hypothesis 1b: lf-rTMS will reduce aberrant functional connectivity in the motor system, e.g. between thalamus and M1. lf-rTMS will alter regional CBF in the motor system and increase SMA and M1 activity during the fMRI task. No relevant changes are expected in the sham group, iTBS may deteriorate neural alterations.

Hypothesis 1c: cortical excitability will be differentially changed with rTMS. Lf-rTMS will increase SIC1, while iTBS will reduce SIC1.

Aim 2: characterization of psychomotor slowing (PS) in schizophrenia spectrum disorders compared to healthy controls

Hypothesis 2a: Patients will have poorer performance on all motor tasks, eg. reduced activity levels, increased postural sway, and less coin rotations

Hypothesis 2b: Patients will have aberrant structural and functional connectivity within the motor system, as well as increased CBF in basal ganglia and decreased CBF in premotor/motor cortex. Applying network metrics, the functional motor network will be less efficient in schizophrenia.

Hypothesis 2c: Behavioral measures of PS will be associated with aberrant motor network structure, perfusion, function, and connectivity. For example, patients with strong PS will have increased resting state functional connectivity between thalamus and M1. PS severity will be linked to reduced structural motor network efficiency, lower M1 and SMA activity during the fMRI task, and increased SMA perfusion at rest.

Hypothesis 2d: Patients will have increased motor cortex excitability (e.g. reduced SICI), which will be linked to measures of PS.

Aim 3 characterize short term dynamics of PS

Hypothesis 3a: in very few subjects we expect relevant spontaneous improvements in PS measures. The majority will have less than 20% fluctuation of motor parameters within 3 weeks

Hypothesis 3b: we expect slight longitudinal changes in resting state functional connectivity and perfusion of the motor system, but no structural changes.

Aim 4: to describe the short-term and medium-term clinical outcome of 3 weeks of rTMS intervention

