11.3 Statistical criteria of termination of trial

No statistical stopping rules are planned.

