11.4.2 Primary Analysis

The primary analysis will be a repeated measures ANOVA of SRRS scores with two timepoints (within

subjects: baseline and week 3) and four groups (lf-rTMS, iTBS, sham, waiting group-If-rTMS). In case of significant baseline demographic or clinical group differences, we will adjust for these in an repeated measures ANCOVA of SRRS.

The analysis will be performed by the PI and his team in SPSS using data from the RedCap database.

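### Section 11.4.4 allows up to seven by-arm looks at the primary SRRS test to guide arm changes, with no alpha adjustment or decision rule, so the type I error is not controlled as written

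*Combined protocol and SAP*

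**What the plan says.** - Section 11.4.4 sets the looks: "Interim analyses of the primary analysis are planned after enrolment of 10, 20, 30, 40, 50, 60, and 70 subjects". Their purpose: "The scope is to estimate whether any adjustments of the treatment arms are necessary". Who decides and who runs them: "All interim analyses are optional and at the discretion of the PI. Interim analyses are conducted by the PI and his team".
- Section 11.4.2 defines what is looked at: "The primary analysis will be a repeated measures ANOVA of SRRS scores with two timepoints", with four groups. A look at the primary analysis is therefore a comparison of SRRS change by arm.
- Section 11: a two-tailed p below .05 "is considered to be statistically significant in all analyses". Section 11.2 sizes the trial for one such test with 88 patients.
- Section 11.1, main hypothesis 1a: "lf-rTMS (inhibitory) will be superior over placebo or iTBS (facilitatory) in all clinical and motor behavioral measures".
- Section 11.3: "No statistical stopping rules are planned". Section 2.9 lists, among examples of grounds for ending the study, "early evidence of benefit or harm of the experimental intervention".
- Section 6.2.1 fixes equal allocation to the four arms over the whole sample. It does not say what happens to allocation if an arm is changed.
- Section 1.6 rules out a data safety monitoring committee. Section 6.1 requires assessors to be blind to treatment.
- Section 5.1 places the primary endpoint at week 3, whereas the looks are triggered by enrolment.

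**The concern.** These are comparative looks at the primary endpoint with a stated use, which is to change the arms. A final test at .05 keeps its level if interim results have no influence on the trial. Once the arms that remain depend on interim SRRS results, the unadjusted final test need not keep that level, and the effect of a selected arm is overestimated. The plan does not say which looks will take place, what result leads to what change, which changes are permitted, or how the final ANOVA is then done. These choices can therefore be made after by-arm results have been seen. Nor does any section say that those results are kept from the outcome raters. At stake is whether a significant primary result can be read at its nominal level.

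**Working it through.** **1. The plan's own figure.** Inputs from section 11.2: f = 0.23, correlation 0.5, 4 groups, 2 time points, alpha .05, power .95. For the group-by-time interaction:

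λ = f² × N × m / (1 − ρ) = 0.0529 × 88 × 2 / 0.5 = 18.6, with df 3 and 84.

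The noncentral F distribution gives power .957. With N = 84, λ = 17.8 and power is .947, so 88 is the smallest equal-arm total that reaches .95. The stated sample size is correct for one fixed test at .05.

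**2. Set-up for the error rates.** With two time points, the group-by-time test equals a one-way ANOVA on change scores. Trials were simulated under the null with normal change scores and 22 patients per arm. Three assumptions are not in the documents: balanced (blocked) allocation, so 10 per arm at 40 patients; complete week-3 data at each look; and each decision rule below, since the plan states none.

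**3. Looks not acted on.** The error of the final four-group test is .050.

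**4. One arm change at 40 patients.** This is the kind of use that section 11.4.4 names. The remaining arms continue to 22 each, and the three-group ANOVA is tested at .05 without adjustment (400,000 null trials).

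| Rule at 40 patients | Error of final test |
|---|---|
| Drop the worst arm | .029 |
| Drop the best or the worst comparator (lf-rTMS kept) | .040 |
| Drop the comparator closest to lf-rTMS | .065 |
| Drop the arm nearest the overall mean | .075 |

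An arm dropped at random leaves the error at .05, so the departures come from using the SRRS data to choose.

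**5. Keep the better of lf-rTMS and iTBS, then test it against sham.** False superiority of the retained arm is .040, against .025 for an arm fixed in advance. Over all trials, about .020 of this is false superiority of lf-rTMS and the other half is false superiority of iTBS. The upward bias in the retained arm's effect follows directly. The expected larger of two interim means is (1/√π) × SD/√10 = .178 SD, and these patients are 10 of the final 22, so the bias is .178 × 10/22 = .081 SD of change.

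**6. Hypothetical rule: any look with p < .05 counts as success.** The documents do not state this rule.

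| Looks, plus final at 88 | Four-group error |
|---|---|
| 40 | .086 |
| 20, 40, 60 | .135 |
| all seven | .197 |

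With patients entering in random order instead of blocks, the figures are .087, .137 and .198.

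**7. One prespecified look instead.** Take an O'Brien-Fleming-type look at 44 of 88 patients with threshold p < .0052 to .0056. A final level of .047 gives a total error of about .050 (1,000,000 null trials); a final level of .048 gives about .051. Power at λ = 18.6 and alpha .047 is .954.

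**The case against.** The strongest reply is that the plan contains no efficacy stop. Section 11.3 plans no statistical stopping rules, and section 11.4.4 gives the looks one purpose, which is to consider arm adjustments. Section 2.9 is a general list of examples and does not mention the interim analyses. A reader might infer from seven looks at .05 that the trial's type I error is about 20%. The documents do not support that, because the figure needs a success rule that they do not contain. Nor do sections 2.9 and 11.3 strictly contradict each other: a study can allow termination on judgement and have no statistical rule. What they leave open is what an interim SRRS result may trigger.

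Inflation is also not certain under arm changes. Several natural rules, such as dropping the worst arm, are conservative. A reader might infer from the .040 in step 5 that false lf-rTMS claims rise above .025. Over all trials they do not, since only about half of the .040 concerns lf-rTMS. The selection bias remains.

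There are safeguards against silent changes. Protocol changes need prior sponsor and ethics committee approval (section 2.3), and deviations from the statistical plan must be reported and justified (section 11.4.6). These make an arm change visible, but they set neither the error rate nor the final test.

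Finally, deleting the looks would remove the only planned by-arm review of SRRS during the trial, because section 11.4.5 covers adverse events only. That is a fair cost, and the fix allows for it.

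**Conclusion.** The concern holds in this form: the type I error of the primary test is not controlled as written, because the plan allows by-arm looks intended to guide arm changes and gives no boundary, decision rule or adjusted final test. It does not follow that the error is inflated. The actual error cannot be calculated. It is .05 if the looks have no consequence, and about .03 to .075 in the arm-change examples at 40 patients. Selecting the better of the two active protocols biases its effect by about .08 SD of change. The values of about .09, .14 and .20 belong only to the hypothetical any-look rule and should not be quoted as the trial's error rate. All figures rest on normal change scores, balanced allocation and complete week-3 data at each look. Real looks triggered by enrolment would contain fewer outcomes. The sample-size arithmetic itself is sound. The plan should be corrected before any look is taken.

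**What to change.** In section 11.4.4, choose one of the following:

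- Delete the by-arm efficacy looks at the primary analysis, or make them blinded and non-comparative.
- Keep one look, triggered by completed week-3 data. Prespecify its decision rule, an O'Brien-Fleming-type boundary, a final alpha of about .047, who runs it, and that by-arm results are withheld from outcome raters.

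In either case, state that no efficacy claim and no efficacy-driven arm change will be made outside that rule. If the rule permits an arm change, it must also specify the allocation and the final test that follow, because the group-sequential boundary alone does not cover that. Make sections 2.9, 11.3 and 11.4.4 say the same thing about what an interim SRRS result may trigger. Safety review and harm-related termination, including any by-arm check for worsening, stay as the sponsor defines them.

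The cost is wording in three sections and the loss of the PI's informal looks at efficacy. If one look is kept, power on the plan's own inputs goes from .957 to .954, still above the planned .95 with 88 patients.
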